6 INTRODUCTION

6.1 Background & Rationale

Actinic keratosis (AK) is a common epithelial non-infiltrative lesion caused by prolonged exposure to ultraviolet (UV) radiation, which damages cell cycle regulators and leads to the proliferation of epidermal keratinocytes. Actinic keratoses are premalignant skin lesions that are characteristically distributed on sun-exposed areas such as face, bald scalp, neck, chest, back of the hands, and forearms. Individuals often present with multiple actinic keratoses.

Actinic keratosis is a global condition and it is the second most frequent diagnosis made by dermatologists in the US (Uhlenhake 2013) with prevalence between 11% and 26% (Salasche 2000). Actinic keratoses themselves are deemed not serious, but they are very common, highly widespread, and recurrent. Actinic keratosis is considered the earliest, clinically recognizable manifestation of squamous cell carcinoma (SCC) that is capable of transforming into SCC (*in situ* and invasive) (Feldman 2011 p201). Between 60-80% of SCC cases begin as AK (Feldman 2011). The rate of progression of AK to invasive SCC has been estimated to be from less than 0.025% to 16% per year (Werner 2013). However, there is no reliable way to measure this rate and predict which lesions will transform, meaning that it is necessary to treat AK lesions to avoid progression.

The etiology of AK is multifactorial, and risk factors include increased age, male gender, a fair skin Fitzpatrick skin type, and extensive outdoor activities (Goldberg 2010). Moreover, AK is an indicator of chronic ultraviolet (UV) damage and thus, of increased risk for UV-related skin cancer. A review of epidemiological studies showed that the prevalence and incidence of AK are highly variable according to the population studied, world location, age, and gender (Frost 1994). For example, prevalence rates near 60% have been reported in Australia, and even up to 64% in women and 83% in men aged 60 to 69 years (Frost 1998; Frost 2000), in contrast to the prevalence rate reported in England in 2000 of 15.4% in men and 5.9% in women older than 40 years (Memon 2000). These rates increased to 34.1% and 18.2%, respectively, at 70 years of age, when prevalence was most strongly related to 2 objective signs of sun exposure, solar elastosis and lentigines. The South Wales Skin Cancer Study reported an AK prevalence of 23% (Harvey 1996). Studies in the United States have reported prevalence rates of 55% in individuals aged 65 to 75 years with high sun exposure, but only 12% to 19% in those with low sun exposure (Engel 1988).

Various treatment options are available for AK lesions, including destructive therapies such as cryosurgery or excisional surgery, topical therapies such as 5-fluorouracil, imiquimod, diclofenac, ingenol mebutate, and non-approved topical or oral retinoids (Gold 2006; Fenske 2010). However, patient satisfaction with many of these treatments, especially the destructive therapies, can be affected by considerable treatment discomfort and residual scarring. Photodynamic therapy (PDT) is a highly efficacious therapy recommended as a first-line treatment for individual, or multiple and/or confluent AK lesions (de Berker 2007; Braathen 2007). Photodynamic therapy has been associated with a better cosmetic outcome than other treatments, and it can also be used to treat multiple AK lesions over large areas (Lehmann 2007; Sidoroff 2010).

Metvixia® cream 168 mg/g (methyl aminolevulinate) was approved in the USA in 2008 (NDA 021415) in combination with LED red light illumination using the Aktilite® CL128 lamp for the treatment of thin and moderately thick, non-hyperkeratotic, and non-pigmented AK of the face and scalp (it was initially approved in 2004 with the Curelight lamp), and was marketed for more than 4 years until it was withdrawn in the United States in 2012 for commercial reasons. The product, used in combination with red light illumination, is also named Metvix or Metvixia in other countries worldwide.

Galderma has developed a new treatment regimen for the face and scalp, in which natural daylight (DL) may replace the previously-approved red light as the means of activating the PpIX formed after application of the cream during PDT.

Given that the area to be treated is no longer limited by the size or configuration of the lamp, the DL-PDT procedure is simplified compared to conventional PDT (c-PDT). In addition, significantly less pain is experienced during illumination as shown in 2 randomized, Phase 3 clinical studies recently conducted by Galderma. These studies, performed in Australia (N=100) and Europe (N=108), confirmed that methyl aminolevulinate hydrochloride (MAL) DL-PDT has similar efficacy as MAL with c-PDT, leads to fewer related adverse events, is nearly painless, and more convenient for subjects (Rubel 2014, Lacour 2015). It is known that the use of the red lamp results in discomfort and pain for subjects, as all produced PpIX is photobleached in a short period of time. With 2 hours of DL exposure, PpIX will be continuously produced at a very low level and immediately photobleached with no or almost no pain.

The use of DL-PDT, as opposed to the use of blue or red light sources c-PDT, has many benefits. In particular, the use of DL will treat whole fields of cancerization to target visible and subclinical AK lesions, and is not limited to clinically apparent lesions. In 2015, an European consensus on DL-PDT (Morton 2015 p1) recommended DL-PDT as a first-line treatment option for immunocompetent patients with Grade I (thin) or II (moderately thick) AKs or fields of actinic damage on the face and scalp, due to its efficacy, tolerability, and simplicity. More recently, a structured Expert Consensus on Actinic Keratosis has confirmed DL-PDT as a valuable option for subjects with multiple AKs in small or large fields (Calzavara-Pinton, 2017).

Methyl aminolevulinate hydrochloride is marketed under various trade names: Metvix / Metvixia / Mexvivia 160 mg/g or 168 mg/g. The products are identical but are labelled differently, depending on the various country specific approvals. As of 30 June 2019, the product is approved in 39 countries for the treatment of AK, basal cell carcinoma (BCC), and Bowen's disease (individual country approvals vary) with a red lamp. As of 30 June 2019, Metvix® Cream with DL activation for the treatment of AK has been approved as a variation to the current Metvix Aktilite authorization in Europe and outside Europe (Argentina, Australia, New Zealand, Singapore, Switzerland, Russian Federation, Colombia, Mexico, Brazil, Costa Rica, Venezuela, Chile, and Canada). In addition, Luxera, Luxerm, and Lumexia are other commercial names for the same product, which is approved for the treatment of AKs with daylight only, approved in Austria, Germany, Italy, Portugal, Spain, and Sweden.

Galderma is developing MAL DL-PDT in the United States for lesion treatment, but may consider field treatment as a secondary indication for life cycle management. This study serves as a follow-up study to RD.06.SPR.112199 to evaluate recurrences of lesions that achieved CR in both MAL cream DL-PDT and vehicle cream DL-PDT treated groups.

1.0

RD.06.SPR.115230 Amendment 2 Protocol V3.0 C

15-Jan-2021 00:00:00

Approved

CONFIDENTIAL

7 STUDY OBJECTIVES & ENDPOINTS

7.1 Primary Objective

The primary objective of this study is to assess recurrence of AKs treated in RD.06.SPR.112199 for those subjects who achieved Complete Response (CR) of treated AK lesions. They will be offered the opportunity to participate in this 9-month long-term follow-up study (i.e., 52 weeks after the last DL-PDT), continuing the double-blind conduct of this study.

7.2 Secondary Objective

The secondary objective of this study is to evaluate the long-term safety of MAL DL-PDT and vehicle cream DL-PDT for 52 weeks after the last DL-PDT for those subjects who achieved Complete Response (CR) of treated AK lesions in study RD.06.SPR.112199.

7.3 Primary Endpoint

- The primary efficacy endpoint is the subject recurrence, defined as the proportion of subjects with recurrence of any (≥ 1) cleared treated AK lesions at Visit 3, 52 weeks after the last DL-PDT treatment.

[figure not shown]
7.4 Secondary Endpoints

- Lesion recurrence, defined as the percent recurrence of cleared treated lesions at Visits 2 and 3, 26 and 52 weeks after the last DL-PDT treatment.
- Subject recurrence, defined as the proportion of subjects with recurrence of any (≥ 1) cleared treated AK lesions at Visit 2, 26 weeks after the last DL-PDT treatment.

7.5 Safety Assessments

- Assess safety, including adverse events (AEs), Treatment-emergent AEs (TEAEs), related to the study drug administered in study RD.06.SPR.112199 and serious AEs (SAEs)

CCI

8 INVESTIGATIONAL PLAN

8.1 Overall Study Design and Plan

This is a double-blind, vehicle-controlled, multicenter, parallel-group long-term follow-up study to evaluate recurrence of AKs in subjects who completed study RD.06.SPR.112199. Only those subjects who achieved CR of treated AK lesions at the Final Visit of that study will be offered the opportunity to continue to be followed in the current study for 9 months to assess recurrence.

In this study, the results of DL-PDT with MAL 16.8% cream or a vehicle cream will be compared; no intervention occurs in this study.

All subjects will provide written informed consent prior to any study-related procedure.

A total of approximately 130 subjects will continue from the study RD.06.SPR.112199 to be followed for another 40 weeks, which corresponds to 52 weeks after the last DL-PDT. It is anticipated that approximately 111 subjects will continue from the MAL cream arm, and 19 subjects will continue from the vehicle cream arm. Blinding will be maintained through this study.

Subjects will have a combined visit which includes the final visit for the RD.06.SPR.112199 study and the initial visit for this study. Data from the previous study will be pulled into the database for this study. Subjects will return to the study center for another visit at Visit 2 (Week 14, 26 weeks after the last DL-PDT treatment) for efficacy and safety assessments. The investigative site staff will contact the subject via telephone at Week 26 (38 weeks after the last DL-PDT treatment) to determine if the subject is experiencing any treatment-related safety issues.

[figure not shown]
The primary endpoint of this study occurs at Visit 3; Final Visit, Week 40 (52 weeks after the last DL-PDT visit).

The 4 planned interactions are:

Visit 1	Rollover visit from study RD.06.SPR.112199; corresponds to Visit 6 in that study. Only those subjects who achieve CR will be given the opportunity to continue in this long-term follow-up study. All assessments captured are transferred to this study
Visit 2	Week 14 (26 weeks after the last DL-PDT treatment) - Efficacy and safety assessments; CCI
Telephone check in	Week 26 (38 weeks after the last DL-PDT treatment) - Safety assessments
Visit 3	Week 40 Final Visit (52 weeks after the last DL-PDT treatment) - Efficacy and safety assessments; CCI

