Study Design: This is a double-blind, multicenter, parallel group, vehicle-controlled long-term follow-up study to evaluate recurrence of AKs in subjects who completed study RD.06.SPR.112199. Only those subjects who achieved CR of treated AK lesions at the Final Visit (12 weeks after the last DL-PDT session) will be offered the opportunity to continue to be followed in the current study for 9 months to assess recurrence. After obtaining informed consent for this follow-up study, the subjects will return at Weeks 14 and 40, which correspond to 26 and 52 weeks after the last DL-PDT session, respectively to assess the lesions treated in the previous study for recurrence of AK. Recurrence will be determined by reappearance of those lesions completely cleared by 2 DL-PDT sessions, i.e., subjects whose lesions are evaluated to be non-CR at the visits in this study will be deemed to have recurrence. If the percentage of subjects maintaining complete response would be 60% at Visit 3 (52 weeks after the last DL-PDT), 40% of subjects would have experienced recurrence (subject recurrence response). The same calculation will be done for lesion complete response, to assess the lesion recurrence. There will be a telephone check-in with the subjects by the clinical site at Week 40 to help retain the subject's participation for the entire duration of the study. CCI

Number of Subjects:

Approximately 111 subjects from the MAL cream arm and 19 subjects from the vehicle cream arm from the previous study are expected to enroll in the follow-up study.

Treatment:

Neither investigational product nor intervention will be part of this study.

Study Duration:

The expected duration for each subject's participation in the study will be approximately 40 weeks from the completion of study RD.06.SPR.112199.

Study Population:

The study population will consist of adult male and female subjects with clinically confirmed mild to moderate actinic keratosis on the face and balding scalp, who have completed study RD.06.SPR.112199 with a Complete Response at Final Visit of that study, meaning those subjects, whose treated AKs were all cleared at 12 weeks after the last DL-PDT session.

Inclusion Criteria: To be eligible for study entry, subjects must satisfy all of the following inclusion criteria:

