8.1.2 Schedule of Assessments

Table 1: Schedule of Assessments

RD.06.SPR.112199

RD.06.SPR.115230

Visit	1	2	2b ^{a,b}	3	4	4b ^{a,b}	5 ^{a,b}	6 ^{a,b}	1	2 (7)	TC	3 (8)
Purpose	Medical history and labs	First DL-PDT session	If required	Follow-up 1 week after 1 st DL-PDT	Second DL-PDT session	If required	Follow-up 1 week after 2 nd DL-PDT	Final 12 weeks after last DL-PDT	Visit 6 is Visit 1 of LTFU study	26 weeks after last DL-PDT	Telephone call to check on subject	Final 52 weeks after last DL-PDT
Week	Screening	Baseline			Week 2		Week 3	Week 14/ET ^c		Week 14 Week 28	Week 26 Week 40	Week 40/ET Week 54
Visit window	-14 to -5 days	0 to +14 days			0 to +14 days		-2 to +14 days	-2 to +28 days		+/- 5 days	+/- 5 days	+/- 5 days
LONG-TERM FOLLOW-UP STUDY												
Informed Consent CCI	X								X			
Demographics (including FST)	X								X			
Medical History	X								X			
Previous Therapies/Procedures	X								X			
Vital Signs/Physical Examination	X							X ^g →	X			
Inclusion/Exclusion Criteria	X	X						X →	X			
Hematology/ Blood Chemistry/ UA/ECG	X							X				
Pregnancy Test ^c	X	X	X		X	X		X →	X	X		X
Weather assessment		X	X		X	X						
CCI												
AK mapping + counting + grading ^d		X	X		X	X		X →	X	X		X
Sunscreen application		X	X		X	X						

Visit	1	2	2b ^{a,b}	3	4	4b ^{a,b}	5 ^{a,b}	6 ^{a,b}	1	2 (7)	TC	3 (8)
Purpose	Medical history and labs	First DL-PDT session	If required	Follow-up 1 week after 1 st DL-PDT	Second DL-PDT session	If required	Follow-up 1 week after 2 nd DL-PDT	Final 12 weeks after last DL-PDT	Visit 6 is Visit 1 of LTFU study	26 weeks after last DL-PDT	Telephone call to check on subject	Final 52 weeks after last DL-PDT
Week	Screening	Baseline			Week 2		Week 3	Week 14/ET ^c		Week 14 Week 28	Week 26 Week 40	Week 40/ET Week 54
Visit window	-14 to -5 days	0 to +14 days			0 to +14 days		-2 to +14 days	-2 to +28 days		+/- 5 days	+/- 5 days	+/- 5 days
Lesion débridement and treatment application		X	X		X	X						
Geolocalized Satellite data and exposure time		X	X		X	X						
Study drug(s) Dispensing (D) and Accountability (A)		X	X		X	X						
Subject Assessment of Pain		X	X		X	X						
Subject Skin Aspect Assessment ^d								X				
Subject satisfaction questionnaire ^d					X	X		X ^d				
Safety Visit Question				X			X					
Adverse Events ^e	X	X	X	X	X	X	X	X [→]	X	X	X	X
Concomitant Therapies/Procedures ^d		X	X	X	X	X	X	X [→]	X	X	X	X
Subjects with Complete Response evaluation and IC for continuation into long-term follow-up study								X				

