Exit form ^f								X				X

Visits 2 and 4 may be delayed for up to 2 weeks in case of unsuitable weather conditions at randomization/treatment outset; these visits will be Visits 2b and 4b. These postponements will be automatically added to the time of scheduled Visits 5 and 6

If subjects experience rain during the 2 hours of daylight exposure of either DL-PDT visit, they will be instructed to go indoors at the investigative site and the study drug will be washed off. The treatment will be considered incomplete and should be repeated at a minimum interval of 2 weeks. There will be only one attempt at retreatment of an incomplete treatment. These visits will be Visits 2b and 4b. If the attempt at retreatment is also incomplete, the subject will not be excluded from the study. Likewise, these repeat visits will be added to the time of scheduled Visits 5 and 6. If a subject has two incomplete visits in a row, the subject will continue with assessment in this study.

- a) Only for females of childbearing potential, UPT at Visits 1,2, and 3 of this study
- b) Should be performed earlier if subject discontinues before Visit 3 of this study
- c) Adverse Events have to be collected from the time of the Informed Consent signature
- d) Exit form should be completed after subject data collection has been completed for subjects in the study; FST=Fitzpatrick Skin Type
- e) Red arrows signify that pertinent data obtained at Visit 6 of RD.06.SPR.112199 will be transcribed as this visit as Visit 1 of RD.06.SPR.115230

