9.1.4. Analysis Visits Definition

Analysis visit will be calculated according to the following table (see Table 5) to summarize the data by proper visit.

Table 5 - Analysis Visits Definition

Clinical Visit	Analysis Visit	Analysis Visit Number	Target Study Day	Visit Window
Visit 1 (12 weeks after the last DL-PDT)	Week 14	11	Day of Visit 6 of study RD.06.SPR.112199	<= Target Study Day + 14 days
Visit 2 (26 weeks after the last DL-PDT)	Week 28	12	Day of last DL-PDT + 182 days	>= Target Study Day - 21 days <= Target Study Day + 21 days
Telephone Contact (38 weeks after the last DL-PDT)	Week 40	13	Day of last DL-PDT + 266 days	>= Target Study Day - 21 days <= Target Study Day + 21 days
Visit 3 (52 weeks after the last DL-PDT)	Week 54	14	Day of last DL-PDT + 364 days	>= Target Study Day - 28 days

Early termination visit will be managed as a stand-alone visit. The assessments performed at early termination visit will be windowed based on the analysis visit windows.

Unscheduled visits will be windowed based on the analysis visit windows.

If multiple assessments are performed within the same window, all assessments will be listed and the ones taken closest to the target study day will be used for the analysis.

This document is confidential.

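### Week numbers counted from Visit 1 match 26 and 52 weeks after the last DL-PDT only if Visit 6 is on time; a late Visit 6 can put an on-schedule Visit 2 outside the SAP window

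*Protocol*

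**What the plan says.** **Table 1 (Protocol 8.1.2).** Each follow-up contact carries two week numbers: 14 and 28 for Visit 2, 26 and 40 for the telephone call, 40 and 54 for Visit 3. The first counts from follow-up Visit 1, which is Visit 6 of the parent study. The second counts from the parent baseline. For Visit 3 the purpose row reads "Final 52 weeks after last DL-PDT" and the week row reads "Week 40/ET Week 54". The window is ±5 days, with no origin stated. Visit 6, labelled 12 weeks after the last session, has a window of −2 to +28 days. On delayed sessions the notes say "These postponements will be automatically added to the time of scheduled Visits 5 and 6"; they do not mention the follow-up visits.

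**Text.** Section 8.1 treats the Visit 1 count and the time since the last session as the same thing: "Subjects will return to the study center for another visit at Visit 2 (Week 14, 26 weeks after the last DL-PDT treatment", and subjects are "to be followed for another 40 weeks, which corresponds to 52 weeks after the last DL-PDT". The synopsis gives the duration as "approximately 40 weeks from the completion of study RD.06.SPR.112199".

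**Telephone call.** The synopsis says "There will be a telephone check-in with the subjects by the clinical site at Week 40", in a paragraph that also uses Week 40 for the 52-week visit. Section 8.1 puts the call at Week 26, 38 weeks after the last session.

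**SAP.** Table 5 (9.1.4) places data only by days since the last session. Visit 2 has the target "Day of last DL-PDT + 182 days" and a window of ±21 days, the call day 266 ±21, and Visit 3 day 364, accepted from 28 days earlier with no upper limit. Under 9.1.5 a subject with missing data is a non-responder, and missing lesion counts are imputed as if every baseline lesion had recurred.

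**The concern.** The endpoints are defined by time since the last DL-PDT session, and the longer a subject is at risk, the more chance a cleared lesion has to return. A site counting 14 and 40 weeks from Visit 1 and a site counting 26 and 52 weeks from the last session would both believe they were on schedule, yet could examine comparable subjects weeks apart.

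The study is descriptive and SAP 9.8.2 plans no sensitivity analysis, so visit timing and the imputation rule feed directly into the reported proportions. If a visit made on one clock falls outside the analysis window drawn on the other, a subject who was seen and found clear could be counted as a recurrence.

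**Working it through.** All days below are counted from the last DL-PDT session unless stated otherwise.

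**1. The plan's own figures.** With Visit 6 at 12 weeks (day 84) and the second session at Week 2 (day 14 from baseline), the three counts agree:

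| Contact | From Visit 1 | From parent baseline | SAP target |
|---|---|---|---|
| Visit 2 | 84 + 98 = 182 | 196 − 14 = 182 | 182 |
| Call | 84 + 182 = 266 | 280 − 14 = 266 | 266 |
| Visit 3 | 84 + 280 = 364 | 378 − 14 = 364 | 364 |

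**2. Visit 6 within its window.** Let Visit 6 be *d* days late, with *d* from −2 to +28, so Visit 6 falls on days 82 to 112. Counted from Visit 1:

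- Visit 2: 82 + 98 − 5 = 175 to 112 + 98 + 5 = 215
- Visit 3: 82 + 280 − 5 = 357 (51.0 weeks) to 112 + 280 + 5 = 397 (56.7 weeks)

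Counted from the last session, Visit 2 is on schedule on days 177–187 and Visit 3 on days 359–369.

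**3. When no date satisfies both.** For Visit 2 the windows are 177 to 187 and 177 + *d* to 187 + *d*. They overlap only if 177 + *d* ≤ 187, that is *d* ≤ 10. The same holds for Visit 3. From *d* = 11 to *d* = 28 there is no common date: 18 of the 31 permitted days. This counts calendar days, not subjects.

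**4. Visit 2 against SAP Table 5.** The analysis window is 182 ± 21, days 161 to 203. Counted from Visit 1:

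- Latest permitted day beyond 203: 182 + *d* + 5 > 203, so *d* ≥ 17
- Nominal day beyond 203: 182 + *d* > 203, so *d* ≥ 22
- Earliest permitted day beyond 203: 182 + *d* − 5 > 203, so *d* ≥ 27 (days 204–214 at *d* = 27, 205–215 at *d* = 28)

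The next window, for the call, opens on day 266 − 21 = 245. An examination on days 204 to 215 therefore belongs to no analysis visit. Unless another assessment falls within days 161–203, the Week 28 value is missing: the subject is imputed as a recurrence and drops out of the observed-case summary.

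**5. Visit 3 against SAP Table 5.** It is accepted from day 364 − 28 = 336 with no upper limit. All of days 357–397 enter the primary analysis, so examinations on days 370–397 are pooled as 52 weeks.

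**6. The Week 28 and Week 54 labels.** If sites schedule by these, with the second session at its full +14 days (day 28 from baseline):

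- Visit 2: 196 − 28 ± 5 = days 163–173, still inside 161–203
- Visit 3: 378 − 28 ± 5 = days 345–355, or 49.3 to 50.7 weeks

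**The case against.** **The endpoint clock is already clear.** Section 8.1, the endpoint definitions and Table 1's purpose row all give time since the last session, and the SAP analyses on that clock. A careful site could infer the anchor. That is fair, but 8.1 and the synopsis also state the 14- and 40-week counts as equivalents, and nothing says which governs when they part.

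**The +28 days may exist only to absorb session delays.** Visit 6 would then stay 12 weeks after the last session and the Visit 1 count would hold. The documents do not say so, and the notes already move Visit 6 for postponements separately. On that reading the Week 28 and Week 54 labels would be the ones to fail. The parent protocol, which governs Visit 6, is not available here.

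**The tolerance is wide and timing is blinded.** The SAP accepts ±21 days at Visit 2, no hypothesis is tested, and nothing suggests that timing would differ by arm. This stands, and limits the importance of the point.

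**Stronger readings that do not hold.**

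- A reader might combine the Week 54 label with a repeat session and conclude that Visit 3 could be on schedule well before 49 weeks. That needs sites to schedule by a label no text tells them to use; SAP Table 5 uses Week 28, 40 and 54 only as names for targets set from the last session. It also needs an assumed repeat date, since only a minimum interval of 2 weeks is given.
- A reader might infer that the postponement note breaks the Visit 1 count. It does not: Visit 6 is Visit 1, so a delay to Visit 6 carries forward in weeks counted from Visit 1.
- A reader might infer that late Visit 3 examinations drop out of the primary analysis. None does.
- A reader might take the synopsis call at Week 40 as a second schedule. It is mainly a label slip: 40 is the call's own number on the parent-baseline count.

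**Conclusion.** The point holds and should be corrected, mainly for the secondary endpoints at Visit 2. If visits are counted from Visit 1, a permitted Visit 6 delay of 17 days or more can put an on-schedule Visit 2 past day 203, and a delay of 27 or 28 days always does. A subject who was examined and may be clear would then be counted as a recurrence at 26 weeks, with all baseline lesions counted as recurred. For the primary endpoint the effect is a looser time point: days 357–397 where days 359–369 were intended, all reported as 52 weeks.

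This rests on three assumptions: that Visit 6's −2 to +28 days is measured from 12 weeks after the last session; that at least some sites count from Visit 1; and that Table 5 is applied as written, with a non-responder meaning a recurrence. The documents give neither the frequency of late Visit 6 dates nor a recurrence rate by time, so the effect on the reported proportions cannot be estimated.

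**What to change.** In Table 1, 8.1 and the synopsis, state that the ±5-day windows for Visit 2, the call and Visit 3 count from the date of the last DL-PDT session, including any Visit 4b. This matches the endpoint wording and the SAP Table 5 targets of days 182, 266 and 364. State that the printed week numbers are nominal labels only. Reconcile the synopsis call at Week 40 with Week 26 (38 weeks after the last session) in 8.1.

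The cost is protocol wording and a memo to sites, with no extra visit. The drawback is a shorter gap between Visits 1 and 2 when Visit 6 was late: at the 28-day limit, 98 − 28 = 70 days instead of 98.
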